5.6.2.2.2. Anti-HBs Antibodies

For participants with positive anti-HBs antibodies at baseline who will reach HBsAg seroclearance (as defined in Section 5.4.3.1), descriptive statistics will be calculated for the change (increase) of anti-HBs antibodies level from baseline at the timepoint when achieving the HBsAg seroclearance by intervention arm. In an additional summary, the change of anti-HBs antibodies level from baseline at Week 48 will be summarized descriptively for the subset of the participants achieving HBsAg seroclearance at any time before or at that given timepoint by intervention arm.

If available, cross-tabulations overtime of quantitative versus qualitative anti-HBs values, respectively, will also be presented.

5.6.2.2.3. Anti-HBe Antibodies

The number and proportion of positive and negative values in anti-HBe antibodies will be summarized over time.

Shift tables from baseline will also be provided over time.

5.6.2.3. Time to Event Endpoints

The time to event endpoints defined in Section 5.6.1.3 will be analyzed using the Kaplan Meier method and Log-Rank test similarly to the time to event endpoints described in the Section 5.5.2.3. No Cox model will be provided for the time to event exploratory endpoints.

5.6.2.4. Relationship between HBsAg and HDV RNA

The relationship between HBsAg and HDV RNA will be explored over time during the intervention and FU phases by providing the following scatterplots and heat maps :

The following correlation coefficients will be calculated by study intervention arm for the different correlation scenarios:

- Pearson's correlation coefficient for two continuous variables.
- Phi correlation coefficient for two binary variables.
- Point biserial correlation coefficient for one binary variable and one continuous variable.

Potential relationship on the selected subgroups defined in Section 2.4.1 will also be explored using the same graphical approach. Graphical display combining individual profiles for HDV RNA and HBsAg over time (and mean by intervention arm) will also be provided.

5.6.2.5. Relationship Between Baseline Characteristics and Efficacy Endpoints

The analysis of correlation between each secondary endpoint at Week 48 and selected subgroup variables for efficacy (see Section 2.4.1 for the list of variables) will be performed using the correlation coefficients described in Section 5.6.2.4 , scatter plots and heat plots.

Analysis of correlation and graphical displays will also be used to explore the relationship between efficacy endpoints and predictive outcomes at early visits.

5.6.2.6. Liver Viral Response

Descriptive statistics on actual values at baseline and Week 24 and changes from baseline at Week 24 may be summarized for the list of parameters described in Section 5.6.1.6 if sufficient biopsy data on Part 2 subjects are collected.

Number of cells may be expressed in original unit and proportions, or ratios may be provided in both original and log₁₀ transformed scales. Change from baseline may be provided in log₁₀ transformed unit. In addition, graphical displays e.g spaghetti plots, scatter plot, box plots may be provided.

5.6.2.7. Liver Immune Response

Descriptive statistics on actual values at baseline and Week 24 and changes from baseline at Week 24 will be summarized for the list of parameters described in Section 5.6.1.7 if sufficient biopsy data on Part 2 subjects are collected.

In addition, graphical displays e.g spaghetti plots, scatter plot, box plots may be provided.

Additional immune cells may be evaluated depending on data availability and clinical interest. Spatial distribution for each cell type at baseline and Week 40 may be graphically evaluated.

6. SAFETY

The Safety Analysis Set will be used for all safety analyses based on pooled data from Part 1 and Part 2 of the study. In addition, selected safety analyses may be reported by study part.

All assessments will be presented by analysis phase and study intervention, unless other specified. All summaries will be descriptive, and no inferential methods will be used to compare intervention arms for safety.

Safety and tolerability will be assessed by evaluating treatment emergent-adverse events (TEAEs), physical examinations, vital signs measurements, clinical laboratory tests (including hematology, blood biochemistry, blood coagulation, and urinalysis), and ECGs.

Continuous parameters will be summarized using the following statistics: number of observations, mean, standard deviation (SD), standard error (SE), minimum, median and maximum, unless specified otherwise. Frequencies and percentages will be used for summarizing categorical (discrete) data.

As a result of the IDMC ongoing periodic safety data reviews to ensure the continuing safety of study participants, additional safety analyses may be generated at the discretion of the Sponsor.

6.1. Adverse Events

6.1.1. Definitions

The verbatim terms used in the CRF by investigators to identify adverse events will be coded using the Medical Dictionary for Regulatory Activities (MedDRA version 21.1 or higher). Treatment-emergent AEs (TEAE) are all AEs with a start date on or after the first administration of study treatment or any ongoing event that worsens in severity, intensity or frequency after the first administration of study treatment. If the event date and/or resolution date is recorded as partial or completely missing, then the imputation rules described in Section 2.5.1 will apply.

6.1.2. Analysis Methods

The adverse events will be summarized by intervention arm and by analysis phase. Adverse events will be allocated to phases based on their start date. If the start date of an event falls between (or on) the start and stop date of a study phase, the AE will be attributed to that phase (treatment-emergent principle). For imputation of partially/fully missing dates please see Section 2.5.1. In

case of a completely missing start date, the event is allocated to the double-blind study intervention phase, except if the end date of the AE falls before the first administration of study treatment (DB Day 1).

An overview table will summarize the incidence of TEAEs classified in the following categories: AEs, serious AEs, related AEs, AEs leading to treatment discontinuation, COVID-19 AEs (serious and non-serious) and fatal AEs by presenting by intervention arm the number and percentage of participants who experienced at least one of such AE. The overview AEs table will be also presented stratified by the subgroup of interests identified in Section 2.4.2.

AE relationship to study treatment is grouped into either related or not related category. A related AE is defined as with possible, probable, or very likely relationship with study treatment; not related, otherwise.

All adverse events will be presented in a descending order by incidence based on all participants (Total column). The following TEAEs tables will be included in the analysis:

- All TEAEs
- Serious TEAEs
- At least grade 3 TEAEs
- At least grade 2 TEAEs and related
- TEAEs leading to treatment discontinuation
- Related TEAEs

All serious TEAE, related TEAE, TEAE leading to death, TEAE leading to discontinuation, TEAE of at least grade 3, or AESIs will be listed separately. Listings will include all information collected on the Adverse Event CRF pages (e.g. information on time of onset, duration of events, time of resolution, concomitant therapies and relationship to study treatment).

For participants reporting rash, a listing with specific grade will be provided and Rash questionnaire will be tabulated by study intervention arm and overall.

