2.1. Analysis Phases and Visit Windows

2.1.1. Analysis Phase

The analysis phases are defined in [Table 1](#) below.

Table 1: Analysis Phases Start and End Dates

Analysis phase	Start date	End date
Screening	The date of signing the informed consent	1 day before the first study agent intake
Double-Blind (DB) Study Intervention	Date of first study agent intake	
If participant did not withdraw from the study and did not discontinue treatment early prior to the projected/actual Week 52 Visit date:
 
Min(Date of Week 52 study agent intake – 1 day, cut-off date*)
 
Otherwise:
 
[Min (Early study withdrawal visit date, study agent discontinuation date) + 5 days^a] or cut-off date*, whichever occurs first

Open-Label (OL) Study Intervention	
If participant has a projected/actual Week 52 Visit date:
 
 – End date of DB study intervention phase + 1 day 
Otherwise:
 
 – Missing 	
If participant did not withdraw from the study prior to the projected/actual Week 144 (Arm 1)/Week 148 (Arm 2) Visit date and did not discontinue treatment early prior to the projected/actual Week 140 (Arm 1)/Week 144 (Arm 2) Visit date:
 
[Min (Date of Week 144 Visit (for Arm 1) or / Date of Week 148 Visit (for Arm 2))+ 5 days^a] or cut-off date*, whichever occurs first
 
if participant withdrew from the study or discontinued treatment between projected/actual Week 52 Visit date + 1 day and projected/actual Week 144 (Arm 1)/Week 148 (Arm 2) Visit date:
 
[Min (Early study withdrawal visit date, study agent discontinuation date)+ 5 days^a] or cut-off date*, whichever occurs first

Follow-up	
If participant did not withdraw informed consent during DB or OL study intervention phases
 
Max (End date of DB study intervention phase, End date of OL study intervention phase) + 1 day
 
Otherwise:
 
Missing
	
If participant entered the Follow-up phase:
 
Max [early study withdrawal visit date, study completion date] or cut-off date, whichever occurs first.
 
Otherwise:
 
Missing

*Cut-off dates will be defined to match the prespecified timepoints for IDMC safety monitoring, interim analysis, the primary analysis and the final analysis, respectively.

^a: Addition of 5 days is only applicable for Adverse Events and Concomitant Medications

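### Adverse events are assigned to phases by start date only, so an event that is treatment-emergent through worsening can be missing from, or misplaced in, the by-phase tables

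*SAP*

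**What the plan says.** The definition in SAP Section 6.1.1 has two limbs. The first covers new onset: "Treatment-emergent AEs (TEAE) are all AEs with a start date on or after the first administration of study treatment". The second adds "any ongoing event that worsens in severity, intensity or frequency after the first administration of study treatment".

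Section 6.1.2 presents adverse events by arm and analysis phase and gives the allocation rule: "Adverse events will be allocated to phases based on their start date". If the start date lies within a phase, "the AE will be attributed to that phase (treatment-emergent principle"). The one exception is that in "case of a completely missing start date, the event is allocated to the double-blind study intervention phase", unless the event ended before first dose.

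Table 1 in Section 2.1.1 sets the phase limits. Screening runs from "The date of signing the informed consent" to "1 day before the first study agent intake". The double-blind phase begins on the "Date of first study agent intake".

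Section 6.1.3 also tabulates adverse events of special interest, with ALT/AST elevations first in its list, by arm and phase.

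**The concern.** The allocation rule implements only the first limb of the definition, although Section 6.1.2 describes it as the treatment-emergent principle. An event that qualifies through the second limb is a TEAE by definition but, on its start date, belongs to a phase before treatment or to no phase. In tables split by phase, the second limb then has no effect.

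The same rule acts at the switch from double-blind to open-label treatment. The design defers active treatment in Arm 2, so an event that starts on placebo and worsens on open-label JNJ-3989 stays in the placebo phase. If the record carries its maximum grade (the SAP does not say), a grade reached on active drug would be shown under placebo.

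At stake are the reported incidences in the by-phase TEAE, grade 3 or higher and special-interest tables of a small trial, where one participant moves a percentage visibly.

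**Working it through.** The SAP gives no figure for this point. The check applies its rules to specific events and then bounds the effect.

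**Rules used:** the TEAE definition (6.1.1), the allocation rule and its exception (6.1.2), the phase dates (Table 1) and the partial-date imputation (2.5.1). Section 2.5.1 completes partial onset dates but never resets onset to the date of worsening.

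| Event, kept on one record | TEAE under 6.1.1? | Phase under 6.1.2 and Table 1 |
|---|---|---|
| Starts Day -10, after consent; worsens Day 30 | Yes, by worsening | Screening |
| Starts before consent; worsens Day 30 | Yes, by worsening | None |
| Starts in double-blind phase; worsens in open-label phase | Yes, by start date | Double-blind only |
| Start date completely missing; did not end before first dose | Cannot be judged by date | Double-blind |

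The first two events have no place in the double-blind columns. The fourth does, so an event of unknown onset is placed more favourably than one documented to have worsened on treatment.

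**How the SAP treats similar data.** Section 6.2.1 judges a laboratory result against its baseline grade, so worsening counts. Section 4.4 lets a concomitant medication belong to more than one phase. Adverse events have neither rule.

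**Bound on the effect.** Inputs: 52 participants in total (Section 1.2), randomised 4:1 (Section 1.5), and safety analyses pooled over Parts 1 and 2 (Section 6).

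- Arm 1: 52 × 4/5 = 41.6, about 42. One participant is 1/42 = 2.4 percentage points.
- Arm 2: 52 × 1/5 = 10.4, about 10. One participant is 1/10 = 10 percentage points.

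These are ceilings per affected participant, because the incidences count participants with at least one event. A participant with another event in the same row leaves that row unchanged. They use numbers randomised. A later phase with fewer participants would give one person more weight; Section 1.5, for example, keeps some Part 2 placebo participants out of the open-label phase. The number of participants affected cannot be derived from the SAP.

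**The case against.** The strongest reply is that the loss depends on a recording convention that the SAP does not show. If the case report form or protocol requires a new AE record at each worsening, the start date is the date of worsening and the rule works. That stands, and it makes the effect conditional. It does not remove the inconsistency: the SAP does not state the convention, and under it the second limb of the definition would be redundant.

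A reader might infer that worsening ALT, the trial's main safety signal, would vanish from the double-blind results. The documents do not support that. Sections 6.2.1 and 6.2.2 derive the worst grade within each phase, including unscheduled assessments, and set it against baseline. Sections 5.5.1.1.11 and 5.5.1.1.12 define biochemical flares and ALT/AST elevations from laboratory values. An ALT rise from grade 1 at entry to grade 3 at Week 8 would appear as grade 3 in the double-blind laboratory tables. Nor does the SAP say that raised ALT at entry is recorded as an adverse event dated in Screening.

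A reader might also take each such event to lower the incidence by about 4 points, using roughly 24 active participants in Part 2 (30 × 4/5; 1/24 = 4.2%). That is not supported either. Safety is primarily pooled, with reporting by part only optional, and the count is of participants rather than events.

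Finally, Section 6.1.2 lists serious, related, fatal, discontinuation, grade 3 or higher and special-interest events without naming a phase restriction, so listings may still show the event. All safety analyses are descriptive. Both points limit the harm but leave the incidence tables uncorrected.

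**Conclusion.** The point holds in a conditional form. Sections 6.1.1 and 6.1.2 do not fit together, and nothing else in the SAP reconciles them. Followed literally, the allocation rule leaves a worsened pre-treatment event out of the double-blind AE and special-interest tables, and keeps an open-label worsening in the double-blind phase.

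This rests on the assumption that a worsened event stays on its original record with its original start date. If worsening always opens a new record, the effect is zero. Otherwise the ceilings of about 2.4 points (Arm 1) and about 10 points (Arm 2) per affected participant apply, with pooled numbers as randomised and no other event in the row. Laboratory analyses are not affected. It is worth correcting because a stated rule would give a wrong count, not merely because detail is missing.

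**What to change.** Amend Section 6.1.2 in one of two ways.

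1. Count any adverse event that worsens in a later phase than the one in which it started as treatment-emergent in the phase containing the date of worsening as well, at the worsened grade. The earlier phase shows only the grade reached there. Apply this to worsening of events that began before first dose (including before consent) and to worsening from double-blind to open-label or follow-up. Wording that re-dates only events qualifying as TEAEs through worsening would not be enough, because an event that starts in the double-blind phase already qualifies by its start date.
2. If it matches the data collection, state that each worsening is entered as a new AE record with its own start date.

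The first option costs a sentence or two and one extra derivation, and needs the date and grade of worsening. Counts at a given grade may rise in one phase and fall in another; for example, higher-grade counts in the double-blind placebo column could drop. The second option costs one sentence.

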6.1.3. Adverse Events of Special Interest

Incidence of treatment-emergent adverse events of special interest will be summarized by intervention arm and analysis phase. The adverse events of special interest include:

- ALT/AST elevations
- Injection Site Reactions
- Renal complications
- Hematologic abnormalities (platelet count, hemoglobin, reticulocytes, neutrophil count)
- Cholesterol increase

The list of all preferred terms belonging to ALT/AST elevations, renal complications, cholesterol increase, and hematologic abnormalities is provided in 0. Injection site reactions will be identified using the eCRF Injection Site Reaction form.

6.2. Clinical Laboratory Tests

6.2.1. Definitions

Laboratory data will be summarized by category of laboratory test. The different categories and laboratory tests used in the analysis are listed in Table 6.

Table 6: Laboratory Parameters

Laboratory Category	Parameters		
Hematology	Platelet count RBC count Hemoglobin Hematocrit Reticulocyte count Reticulocyte index	RBC Indices: Mean corpuscular volume Mean corpuscular hemoglobin Mean corpuscular hemoglobin concentration	WBC count with Differential: Neutrophils Lymphocytes Monocytes Eosinophils Basophils
Blood Coagulation	Activated partial thromboplastin time International normalized ratio Prothrombin time		
Clinical Chemistry	Sodium Potassium Chloride Bicarbonate Blood urea nitrogen Creatinine Glucose AST/Serum glutamic-oxaloacetic ALT/Serum glutamic-oxaloacetic Gamma-glutamyltransferase (GGT) Total, conjugated and unconjugated bilirubin Alkaline phosphatase Creatine phosphokinase	Lactic acid dehydrogenase Uric acid Calcium Phosphate Albumin Total protein Total cholesterol High-density lipoprotein cholesterol Low-density lipoprotein cholesterol Triglycerides Magnesium Lipase Amylase	
	Note: Creatinine clearance (eGFR calculated by the CKD-EPI formula) will be assessed.		
Routine Urinalysis	Dipstick Specific gravity pH Glucose Protein Blood Ketones Bilirubin Urobilinogen Nitrite Leukocyte esterase	Sediment (if dipstick result is abnormal) RBCs WBCs Epithelial cells Crystals Casts Bacteria	
Urine Chemistry (quantitative measurement)	Creatinine Sodium Phosphate	Glucose Protein Albumin	
Renal Biomarkers	Retinol binding protein Beta-2-microglobulin		

The laboratory abnormalities will be determined according to the criteria specified in the DAIDS Toxicity Grading Scale (see Clinical Protocol Appendix 8, DAIDS Table) or in accordance with the normal ranges of the clinical laboratory if no gradings are available.

An assessment is treatment-emergent if the toxicity grade/abnormality worsened as compared to the grade/abnormality at baseline; this also includes the shift from abnormally high to abnormally low and vice-versa. Post-reference toxicities/abnormalities are always treatment-emergent with regard to missing toxicities/abnormalities at baseline. The abnormalities ‘Abnormally high’ and ‘Abnormally low’ are considered equally important.

For each lab parameter, a worst-case analysis will be performed by using the worst abnormality and/or worst toxicity grade lab value and time point per participant. The worst toxicity case is the value associated to the highest toxicity grade and is derived per parameter and toxicity direction (low / high). Worst-case will be derived within each phase, including unscheduled assessments. For abnormalities, in case the same subject has both abnormalities (low and high) for the same lab test within the same phase, the participant will be counted in the analysis for both toxicity directions (abnormally high and low).

Imputation rules:

In case continuous laboratory results are not numerically expressed, but as a character (e.g. ‘less than 2’, ‘>25’), these results will be numerically imputed as follows:

- If the analysis result contains '<' then the result will be multiplied by 0.999 (e.g. <6.1 becomes 6.0939).
- If analysis result contains '>' then the result will be multiplied by 1.001 (e.g. >6.1 becomes 6.1061).
- If analysis result contains '≤' or '≥' then only the numeric portion of the result will be used.

This also applies to normal limits expressed as such.

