2.2. Baseline

In general, the baseline assessment is defined as the last observed non-missing measurement before the date and time of the first administration of any of study treatments.

In case the first administration time is missing, the first observed measurement on DB Day 1 will be used as the baseline measurement. If no observed measurement on DB Day 1, the last observed measurement before DB Day 1 will be used as the baseline assessment.

An additional reference timepoint (RT) will be used for an additional analysis of selected efficacy endpoints for Part 2 relative to the actual duration of treatment with JNJ-3989 as motivated by the deferred treatment design. This is described in Section 5.5.1.4.

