5.5. Other Secondary Endpoints

Other secondary endpoints will be summarized descriptively by intervention arm, by study phase (unless specified otherwise), timepoint and study part. No imputation rule will be used in case of missing data and the analysis will be based on observed cases. Statistical analyses of selected other secondary endpoints will be done with no adjustment for multiplicity.

The following on and off-treatment periods will be used for all secondary efficacy endpoints:

- For all HBV endpoints:
 - **On-treatment** will be defined as the time periods in which the participant receives any of the study interventions (JNJ-3989/placebo and/or NA).
 - **Off-treatment** will be defined as the periods when the participants do not receive any of the study interventions (JNJ-3989/placebo and NA).
- For all HDV endpoints:
 - **JNJ-3989 on-treatment** will be defined as the time period in which the participant receives JNJ-3989/placebo (regardless of continuing NA treatment).
 - **JNJ-3989 off-treatment** will be defined as the time period in which the participant is not receiving JNJ-3989 (regardless of continuing NA treatment).

The following on and off-treatment nadirs will be used for all secondary efficacy endpoints:

- **On-treatment nadir** will be defined as the lowest value during the on-treatment period up to the time of assessment.
- **JNJ-3989 on-treatment nadir** will be defined as the lowest value during the JNJ-3989 on-treatment period up to the time of assessment.
- **Off-treatment nadir** will be defined as the lowest value during the off-treatment period up to the time of assessment.
- **JNJ-3989 off-treatment nadir** will be defined as the lowest value during the JNJ-3989 off-treatment period up to the time of assessment.
- **Overall nadir** will be defined as the lowest value collected during the study up to the time of assessment.

A confirmed criteria means that the criteria should be fulfilled at 2 or more consecutive time points or at the last observed time point.

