6.4. Electrocardiogram

6.4.1. Definitions

Evaluation of the triplicate 12-lead ECGs will be based on the mean value of the triplicate parameters and the abnormalities will be defined on the triplicate means.

The following ECG parameters measurements will be analyzed:

- PR interval (ms)
- Heart Rate (bpm)
- QT interval (ms)
- QRS duration (ms)
- QTc Corrected (Fridericia's formula QTcF)

The abnormalities in ECG parameters will be determined according to the criteria specified in the Cardiovascular Safety – Abnormalities Table (see Clinical Protocol Appendix 6, Cardiovascular Safety- Abnormalities Table). Abnormalities on actual values are provided for HR, PR, QRS and QTcF. Additional abnormalities on change from baseline will be provided for QTcF. No abnormalities will be defined for actual uncorrected QT values. Uncorrected QT \geq 500 ms will be flagged and only shown in listings.

An assessment is treatment-emergent if /abnormality worsened as compared to the abnormality at baseline; this also includes the shift from abnormally high to abnormally low and vice-versa. Post-reference abnormalities are always treatment-emergent with regard to missing abnormalities at baseline. The abnormally high values (i.e. abnormally high, borderline prolonged, prolonged, pathologically prolonged) versus the abnormally low values are considered equally important. Abnormalities defined on changes from baseline are always treatment-emergent.

For each parameter, a “worst-case” analysis will be performed by using the worst abnormality and time point per participant. Worst-case will be derived within each phase, including unscheduled assessments. In case the same subject has both abnormalities (low and high) for the same test within the same phase, the participant will be counted in the analysis for both abnormality directions (abnormally high and low).

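### Arm 2's Week 52 reference covers only selected Part 2 efficacy endpoints, so its open-label lab, ECG and vital-sign abnormalities are judged against the pre-placebo value and its HDV nadir carries over from placebo

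*SAP*

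**What the plan says.** **Reference value.** In SAP 2.2, "the baseline assessment is defined as the last observed non-missing measurement before the date and time of the first administration of any of study treatments". For Arm 2 this precedes the 52 weeks of placebo + NA described in 1.2. The same section adds that "An additional reference timepoint (RT) will be used for an additional analysis of selected efficacy endpoints for Part 2". Section 5.5.1.4 sets it at Week 52 for Arm 2 and lists its endpoints, which include changes in HDV RNA, ALT, HBsAg and liver stiffness.

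**Safety rules.** For laboratory tests (6.2.1), "An assessment is treatment-emergent if the toxicity grade/abnormality worsened as compared to the grade/abnormality at baseline". For ECG (6.4.1), "An assessment is treatment-emergent if /abnormality worsened as compared to the abnormality at baseline". Vital signs (6.5.1) follow the same rule. In all three, worst cases are taken phase by phase; for laboratory tests, "Worst-case will be derived within each phase, including unscheduled assessments". Section 6 pools Parts 1 and 2 and presents results by phase and intervention. No safety section names a Week 52 reference.

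**Phase boundary.** In Table 1 the double-blind phase of a participant still on treatment ends the day before the Week 52 injection. The open-label phase starts at "End date of DB study intervention phase + 1 day". Table 2 lists the Week 52 visit under the open-label phase.

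**HDV periods.** In 5.5 the JNJ-3989 on-treatment period "will be defined as the time period in which the participant receives JNJ-3989/placebo (regardless of continuing NA treatment", whereas the off-treatment period "will be defined as the time period in which the participant is not receiving JNJ-3989". The on-treatment nadir is the lowest value in the first of these periods up to the assessment. It sets the threshold for HDV breakthrough in 5.5.1.1.3.

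**The concern.** The deferred-treatment design gives Arm 2 a second treatment start. The SAP recognises this for efficacy, where it supplies a Week 52 reference, but not for the safety tables that are also reported by phase. A reader of those tables will take Arm 2's open-label column as what happened on JNJ-3989. As written, that column partly reflects what changed during the placebo year.

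Two safety outputs can also disagree. Adverse events go to a phase by start date (6.1.2). An abnormality that starts at Week 40 on placebo and lasts to Week 56 would be a double-blind adverse event, yet also an open-label treatment-emergent laboratory abnormality.

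The study is now descriptive, so these tables are themselves the result. Elevations of ALT were seen in about half of the Part 1 participants enrolled when SAP Amendment 3 was written, so attribution of abnormalities to JNJ-3989 will be read closely.

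The HDV wording raises the same issue. Arm 2's placebo year satisfies both the on-treatment and the off-treatment definition, and a low value on placebo can later serve as the nadir for a breakthrough on JNJ-3989.

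**Working it through.** The SAP states no figure on this point, so there is none to reproduce. The check traces the definitions and counts their consequences.

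**1. Effect of the reference on the treatment-emergent flag.** Let g1 be the grade at Day 1, g52 the grade before the first JNJ-3989 injection, and w the worst open-label grade, each from 0 to 4. There are 5 × 5 × 5 = 125 patterns. The SAP flags w > g1; a Week 52 reference would flag w > g52.

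| Pattern | Condition | Count |
|---|---|---|
| Flagged under both | w > g1 and w > g52 | 30 |
| Flagged only against Day 1 | g1 < w ≤ g52 | 20 |
| Flagged only against Week 52 | g52 < w ≤ g1 | 20 |
| Flagged under neither | w ≤ g1 and w ≤ g52 | 55 |

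Example of the second row: grade 0 at Day 1, grade 2 at Week 52 on placebo, open-label worst grade 2. Example of the third: grade 3 at Day 1, grade 1 at Week 52, open-label worst grade 3. The rules differ in 40 of 125 patterns, equally in both directions. These are counts of possible patterns, not expected event rates.

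**2. Phase boundary.** Double-blind end = Week 52 injection date − 1 day. Open-label start = double-blind end + 1 day = Week 52 injection date. A pre-dose sample drawn that day is therefore an open-label value and can be the open-label worst case. Table 5, meanwhile, matches Arm 2's Week 52 to Arm 1's baseline. This step assumes that the sample is drawn on the injection day; one drawn earlier would fall in the double-blind phase.

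**3. Number affected.** With 22 participants in Part 1 and 30 in Part 2 (1.2) at 4:1, Arm 2 has about 22/5 = 4.4 and 30/5 = 6, together 10.4. Part 2 placebo participants with HBsAg >10,000 IU/mL at screening or baseline do not roll over (1.5). The SAP does not say how many there are. If none, one misclassified participant moves the open-label proportion by 100/10.4 = 9.6 percentage points. If, at the extreme, all six, the figure is 100/4.4 = 22.7 points. Early discontinuation would shrink the denominator further.

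**4. Direction of the nadir carry-over.** With log10 values, nadir m and L = log10(63), the first breakthrough threshold is m + 1 if m ≥ L, and L + 1 otherwise. It never falls as m rises. Adding placebo visits can only lower m or leave it unchanged, so the threshold can only fall or stay. The same holds for the 2 log10 version. Carry-over can therefore add breakthroughs and cannot remove any. In 200,000 arbitrary value triples, 27,099 gained a breakthrough and none lost one; that shows direction, not frequency.

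**The case against.** Several points against the concern stand.

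- **Week 52 is not ignored.** A reader might infer that Arm 2 gets no new reference at all. Sections 2.2 and 5.5.1.4 rule that out for selected Part 2 efficacy endpoints, ALT change among them. The gap is one of scope: safety tables, nadirs and Part 1.
- **ALT has better rules elsewhere.** ALT/AST elevations (5.5.1.1.12) and biochemical flares (5.5.1.1.11) compare with the lowest value seen up to that point and have explicit start dates. Adverse events are phased by onset. Section 5.6.1.8 is devoted to on-treatment ALT elevations. The SAP does not support the inference that it would overlook true ALT elevations on JNJ-3989.
- **The unflagged worsening is not invisible.** Section 6.2.2 tabulates the worst grade in each phase whether or not it is emergent, and summarises observed values by visit. Only the flag is lost. However, the abnormality listing is restricted to parameters with a treatment-emergent finding, so it may not show such a case.
- **Arm 2 is not the only before/after evidence.** Each Arm 1 participant has a value before JNJ-3989, alongside a concurrent randomised placebo arm.
- **One study baseline is conventional**, and safety is descriptive. This supports keeping the Day 1 tables, but not having them alone.

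A large numerical claim about breakthrough is also tempting. Assume stationary log10 HDV RNA, 13 placebo visits, within-person SD 0.5 and autocorrelation 0 or 0.5. Over Weeks 52 to 56, a confirmed rise of more than 1 log10 above the nadir then occurs in about 27% with carry-over and 1–2% with a restart. That contrast reflects the short window, in which a restarted nadir has very few values. Over 26 assumed open-label visits (Weeks 52 to 148) the figures are about 95% and 84–86%; at SD 0.3 they are 27–35% and 16–21%. Most of the false rate comes from the running-nadir rule under the assumed noise. The SDs have no source in the SAP, so no size can be claimed.

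Finally, including placebo in the on-treatment period gives the arms comparable double-blind periods, and the off-treatment HDV endpoints are tied to end of treatment or follow-up. That limits the damage from the overlapping definitions but does not resolve which nadir applies after the switch.

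**Conclusion.** The point holds in a limited form. Arm 2's open-label treatment-emergent laboratory, ECG and vital-sign abnormalities are judged against a value taken before a year of placebo. This can credit placebo-period worsening to the JNJ-3989 phase, or leave a worsening after the switch unflagged. The phase boundary adds a smaller fault if the Week 52 sample is drawn on the injection day. ALT/AST elevations, biochemical flares and adverse events are less affected.

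At most about 10 participants are concerned, and each misclassification is worth about 10 to 23 percentage points of Arm 2's open-label incidence, depending on how many roll over. How often it will occur cannot be derived from the SAP.

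The HDV wording is a separate ambiguity. It makes the placebo year both on- and off-treatment and can only add open-label breakthroughs, by an unknown amount. The primary endpoint and the randomised Week 48 comparison are untouched. The correction is worth making because it is cheap and these tables will be read as JNJ-3989 experience.

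**What to change.** 1. In 2.2, 6.2, 6.4 and 6.5, define for Arm 2 in both parts an open-label safety reference: the last value before the first JNJ-3989 injection. Add treatment-emergence, shift and change tables against it, and keep the Day 1 tables.
2. For worst-case derivation, assign Week 52 samples taken before the injection to the double-blind phase, and say so beside Table 1.
3. In 5.5, start Arm 2's JNJ-3989 on-treatment period and its nadir at the first JNJ-3989 injection. Give the placebo period its own name, and require earlier JNJ-3989 exposure before any time counts as off-treatment.

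The cost is some SAP wording, one extra reference flag in programming and one more set of Arm 2 open-label safety tables. No new data are needed.
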